14. Centralized registration of eligible subjects will be completed according to a process defined by the Sponsor. During Part 1 of the study, subjects will be registered by the Medical Monitor to one of the treatment arms; during Part 2, subjects will be randomly assigned to a treatment arm.
15. Appropriate cancer staging procedures should be performed during screening. For the purpose of this clinical trial, the following imaging is expected at screening:
 - a. CT of the chest, and CT (or MRI) of the abdomen
 - b. MRI (or CT) of the brain, if brain metastasis are known or suspected
 - c. CT or MRI of other anatomical regions as clinically indicated

All imaging should be of diagnostic quality and include IV contrast. PET imaging is an acceptable alternative modality provided the CT component is of diagnostic quality as per RECIST 1.1 guidelines.

For subjects with measurable lesions, target lesions should be selected and measured as per mRECIST v1.1 guidelines. ([Appendix 4](#)) Lesions that will be/are injected with INXN-2001 and/or biopsied should not be selected as target lesions, but should be assessed qualitatively as non-target lesions.

Disease sites are to be imaged throughout the study using the same method(s) used at screening. Chest and abdomen imaging are required for all follow-up imaging time points; images of the brain and other anatomical regions should be acquired on follow-up if positive at screening and as clinically indicated.

Tumor response assessments will occur at 12 weeks and 16 weeks (C5D1 and C6D7), and the Follow-up Tumor Assessment visit (24 weeks) for all subjects, including those who may have experienced a dose delay. In the setting of this immunotherapy, a progression observed at week 12 requires confirmation at week 16. Additional tumor response assessments may occur at the discretion of the investigator.

16. A blood sample(s) for cytokine profiling, breast cancer-associated biomarker levels (eg, MUC-1), and also INXN-1001 levels. Please refer to the Laboratory Manual for details regarding sample processing and shipment.

Screening (post-registration)

Cycle 1 - Days 2, 3, 7, and 15

Cycle 3 - Days 2, 3, 7, and 15

[figure not shown]
Cycle 5 - Day 1 (to coincide with the tumor assessment)

Cycle 6 - Days 2, 3, 7, and 15

Post-treatment Safety Assessment

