5.1 Inclusion Criteria

To be enrolled in the trial, each subject must satisfy all of the following inclusion criteria:

1. Males or females of all races \geq 18 years of age, who have provided written informed consent prior to completing any study-specific procedure.
2. Histologically or cytologically confirmed adenocarcinoma of the breast, either locally recurrent or metastatic disease with injectable lesions, for which no proven curative therapy exists. Locally recurrent disease must not be amenable to surgical resection or radiation with curative intent.
3. Subject has failed or progressed on at least 1 prior systemic chemotherapy regimen \pm biologic/experimental therapy (if first-line therapy, failure or progression during or within the first 30 days).
4. Resolution of all chemotherapy or radiation-related toxicities to Grade 1 severity or lower, except for stable sensory neuropathy \leq Grade 2 and alopecia.
5. A minimum of 2 lesion(s) assessed by imaging using mRECIST v1.1. 1 or more lesions NOT to be injected AND at least 1 injectable lesion(s) (eg, may use radiographically-guided injection of lesions if available at site)
6. Eastern Cooperative Oncology Group (ECOG) performance status 0, 1, 2
7. Male and female subjects must agree to use a highly reliable method of birth control (expected failure rate less than 5% per year) from the screening visit through 28 days after the last dose of study drug. Women of childbearing potential (perimenopausal

women must be amenorrheic for at least 12 months to be considered of non-childbearing potential) must have a negative pregnancy test at screening.

8. Adequate bone marrow reserve as indicated by:
 - a) Absolute neutrophil count (ANC) $> 1500/\mu\text{L}$ (without use of growth factors within 7 days)
 - b) Absolute lymphocyte count (ALC) $> 700/\mu\text{L}$ (without use of growth factors within 7 days)
 - c) Platelet count $> 100,000/\text{mm}^3$ (without transfusion in prior 7 days)
 - d) Hemoglobin $> 9.0 \text{ g/dL}$ (without transfusion in prior 7 days)
9. Adequate renal function as evidenced by eGFR using the Modification of Diet in Renal Disease (MDRD) equation: $\text{eGFR} \geq 60 \text{ mL/min}/1.73 \text{ m}^2$
10. Adequate liver function as evidenced by the following:
 - a) Bilirubin ≤ 1.5 times the upper limits of normal (ULN)
 - b) ALT and AST $\leq 2.5 \times \text{ULN}$, in the case of liver metastases $\leq 5 \times \text{ULN}$

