13.4 Appendix 4: Modified RECIST Criteria

Progression-free survival (PFS) rate and response to treatment will be determined on the basis of RECIST v.1.1³⁵ as applied to this trial, taking into account response patterns that have been observed with immunotherapies. In studies with a diversity of immunotherapies in different cancer types, objective responses have been shown to occur after an initial increase in tumor burden characterized as PD by World Health Organization or RECIST criteria.³⁶

The 4 observed patterns of response to immunotherapy in subjects with advanced cancer have been:

1. Immediate response - response in baseline lesions-evident by week 12, with no new lesions
2. Durable stable disease - which in some subjects was followed by a slow, steady decline in total tumor burden
3. Response after initial increase in tumor burden
4. Response in the presence of new lesions - a reduction in total tumor burden during or after the appearance of new lesion(s) at time points later than week 12

To capture these response patterns observed with some immunotherapeutic agents, a modification of RECIST v1.1 (mRECIST) will be utilized.

At Baseline:

The disease burden at baseline will be categorized into target and non-target lesions.

A maximum of 5 target lesions (no more than 2 target lesions per organ), representative of all involved organs, may be selected.

Target lesions are lesions that can be accurately measured in at least one dimension and whose minimum lesion size is as follows:

- Non-nodal lesions ≥ 10 mm or ≥ 2 times the slice thickness/reconstruction interval
- Nodal target lesions (lymph nodes): the short axis must measure ≥ 15 mm irrespective of modality/scanner type and slice thickness/interval

Lesions that are/will be injected with INXN-2001 and/or biopsied should not be selected as target lesions.

At Each Subsequent Assessment:

Target lesions are measured at every time point and an overall Sum of Diameters (SOD) will be determined by adding the longest diameters of all non-nodal lesions and short axes (ie, widest dimensions perpendicular to the long axes) of nodal lesions.

Target lesions are assessed as Complete Response (CR), Partial Response (PR), Stable Disease (SD), Progressive Disease (PD), or Not Evaluable (NE) at every time point based on the SOD.

Target Lesion Assessment	Definition

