Complete Response (CR)	CR is declared if all of the following are true for target lesions: 
• The disappearance of all non-nodal target lesions• Any pathological lymph nodes must have a reduction in short axis to <10 mm.
Partial Response (PR)	PR is declared if there is a decrease of at least 30% in the sum of diameters of target lesions taking as reference the baseline sum of diameters of target lesions.
Progressive Disease (PD)	PD is only declared if all of the following are true for target lesions: 
• SOD of all target lesions increases at least 20% taking as reference the smallest SOD recorded at or after baseline• Actual SOD increase is ≥ 5 mm from the smallest SOD recorded at or after baseline
Stable Disease (SD)	SD is declared if target lesion assessment does not meet criteria for PR, PD or CR

Selection and Assessment of Non-Target Lesions:

Non-target lesions are all other lesions, including additional potentially measurable lesions and truly non-measurable lesions, such as lesions that are/will be injected with INXN-2001 and/or biopsied, all bone lesions, ascites, pleural and pericardial effusion, inflammatory breast disease, lymphangitic involvement of skin or lung, and brain lesions. Non-target lesions will be assessed qualitatively, and the possible assessments are CR, Non-CR/Non-PD (NN), and PD.

If pleural effusions or ascites (selected as non-target lesions at baseline) are stable in size or minimally enlarging, they will be assessed as NN. New fluid collections or any effusion that significantly worsens will be considered a sign of PD unless cytopathology results are available that support a non-malignant nature.

Non-target lesions should only be assessed as PD if the progression is unequivocal. In the setting of a subject who also has measurable disease, there must be an overall level of substantial worsening in the context of the overall disease burden. A modest increase in size of one or more non-target lesions is not considered sufficient to qualify for unequivocal progression status. In the absence of measurable disease, the change in the overall non-measurable disease burden should be comparable to at least a 20% increase in overall diameter or 73% in approximate overall volume.

New Lesions:

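### Appendix 4 joins the two minimum sizes for non-nodal target lesions with 'or', so thin slices admit targets under 10 mm for which the 5 mm progression rule is harder to meet

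*Protocol*

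**What the plan says.** Protocol Appendix 4 (Section 13.4) sets two conditions for a target lesion. The general one is "Target lesions are lesions that can be accurately measured in at least one dimension". The size condition for non-nodal lesions is at least 10 mm or at least "2 times the slice thickness/reconstruction interval". Nodes have a fixed floor of 15 mm short axis, "irrespective of modality/scanner type and slice thickness/interval".

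In the same appendix, target PD needs two things together: a rise of at least 20% in the sum of diameters (SOD), and a rise of at least 5 "mm from the smallest SOD recorded at or after baseline". For response, "PR is declared if there is a decrease of at least 30% in the sum of diameters of target lesions", measured from baseline, with no minimum in millimetres.

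Inclusion criterion 5 (Section 5.1) reads "A minimum of 2 lesion(s) assessed by imaging using mRECIST v1.1", and at least one of these must be left uninjected. Injected or biopsied lesions should not be chosen as targets. The imaging instructions (footnote 15 to Tables 2A and 2B; Section 6.4.3) give no slice thickness; footnote 15 says "All imaging should be of diagnostic quality and include IV contrast". The SAP describes a different, single-arm study and does not settle the point.

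**The concern.** Two minimum sizes protect measurement only if both must be met. Joined by 'or', the 10 mm floor never binds on slices under 5 mm, and the slice rule never binds on slices over 5 mm. With about 30 centers and no stated slice thickness, the effective floor can differ from scanner to scanner.

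Two separate endpoints are exposed:

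- **16-week PFS rate.** On a small SOD the 5 mm condition, not the 20% condition, decides target PD. Late PD adds to the number counted progression-free, which is the number compared with the Simon cut-offs.
- **ORR and duration of response.** Thirty percent of a small diameter is a small distance, so measurement noise can produce a PR.

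**Working it through.** **1. The plan's own figures.** Lesion size does not enter the sample size in Section 8.1. Exact two-stage binomial sums, using the final cut-offs in the Synopsis and leaving out Arm A's extra look at 6 subjects, give:

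- Arm A (at least 3 of 13, then at least 9 of 33; 15% against 35%): alpha 4.1%, power 80.8%.
- Arm C (at least 6 of 12, then at least 15 of 26; 40% against 65%): alpha 4.7%, power 80.9%.

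The stated 80% power at one-sided 5% is reproduced and does not change with this point.

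**2. Floor and thresholds for a single target.** Slice thickness is assumed, 1 to 7.5 mm.

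- Floor as written = min(10, 2 × slice).
- Rise needed for target PD = max(20% of SOD, 5 mm).
- Fall needed for PR = 30% of SOD.

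| Slice (mm) | Smallest target (mm) | Rise for target PD | Fall for PR (mm) |
|---|---|---|---|
| 1 | 2 | 5 mm = 250% | 0.6 |
| 2 | 4 | 5 mm = 125% | 1.2 |
| 2.5 | 5 | 5 mm = 100% | 1.5 |
| 3 | 6 | 5 mm = 83% | 1.8 |
| 4 | 8 | 5 mm = 62.5% | 2.4 |
| 5 | 10 | 5 mm = 50% | 3.0 |
| 7.5 | 10 (10/7.5 = 1.3 slices) | 5 mm = 50% | 3.0 |

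The 5 mm condition binds whenever 5/SOD exceeds 20%, that is, for any nadir SOD under 25 mm. Two 5 mm targets (SOD 10 mm) need 50%. Five (SOD 25 mm) need 20%, so the rule no longer bites.

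**3. How sensitive the decision rule is (illustration only).** If a fraction f of true progressors were counted progression-free, the null rate p0 becomes p0 + (1 − p0)f.

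| f | Arm A null rate | Arm A chance of passing | Arm C null rate | Arm C chance of passing |
|---|---|---|---|---|
| 0 | 15% | 4.1% | 40% | 4.7% |
| 2% | 16.7% | 7.3% | 41.2% | 6.1% |
| 5% | 19.25% | 14.4% | 43% | 8.6% |

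The documents give no value for f.

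**4. False PR in an unchanged lesion.** Let d be the SD of the difference between two readings, assumed 1 to 2 mm. One reading: Φ(−0.3 × SOD/d).

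- 5 mm: Φ(−1.5) = 6.7% to Φ(−0.75) = 22.7%.
- 10 mm: Φ(−3) = 0.1% to Φ(−1.5) = 6.7%.

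Section 8.4.2 requires confirmation at least 4 weeks later. Both comparisons share the baseline reading, so with equal reading errors their correlation is 0.5. The bivariate normal probability that two given visits both read PR is:

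- 5 mm: 1.8% to 10.4%.
- 10 mm: under 0.1% to 1.8%.

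With k equal lesions of L mm the single-reading probability is Φ(−0.3kL/(d√k)). Two 5 mm lesions give 1.7 to 14.4%; five give under 0.1 to 4.7%.

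**The case against.** The strongest case against has five parts.

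- **False PR and the primary endpoint.** A reader might infer that noisy PRs inflate the 16-week PFS rate or the Simon counts. They do not. Under Section 8.4.1 a subject counts by not having progressed or died, so PR and SD count alike. This stands in full.
- **Measurement error.** A reader might take it as fact that a 30% fall on a small lesion lies within measurement error. The documents quantify neither that error nor the slice thickness. For one 5 mm lesion the statement fails at the 95% level once d is below 1.5/1.96 = 0.77 mm, and it weakens as lesions are added or responses confirmed. This stands.
- **Small lesions do not create the PD problem.** The 5 mm condition already binds below an SOD of 25 mm, and a single 10 mm target still needs 50% growth after the fix. This stands; small targets only make it worse.
- **PD has other routes.** Non-target progression and new lesions also give PD. This stands in part. With measurable disease, non-target PD needs substantial worsening of the overall burden, and new lesions must be unequivocal and clinically significant, so these routes need not make up for a late target PD.
- **The accuracy requirement.** A target must also be accurately measurable, so the slice rule alone does not qualify a lesion. True, but the requirement has no number and leaves the floor to each reader.

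**Conclusion.** The wording defect is real. As written, the smaller limit suffices, and nothing else in the Protocol sets a numerical floor for non-nodal targets. For a single 5 mm target on 2.5 mm slices, target PD needs 100% growth instead of 50% at 10 mm. This can delay PD and push the 16-week PFS rate upward. By how much cannot be estimated, because the documents do not say how many subjects would have a single small target or what slices the centers use.

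The response effect is separate and confined to ORR and duration of response: about 1.8 to 10.4% false confirmed PR for one unchanged 5 mm lesion at two given visits, against under 0.1 to 1.8% at 10 mm. It rests on an assumed repeat-difference SD of 1 to 2 mm, normal errors and a shared baseline reading; more visits would raise it somewhat. The documents support neither a claim that the primary result would be biased by a stated amount nor a claim that false responses feed the Simon decision. What they support is correcting a measurement rule behind the primary endpoint.

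**What to change.** In Appendix 4, require both limits for non-nodal targets: at least 10 mm and at least twice the slice thickness or reconstruction interval, whichever is greater. The floor then becomes 10 mm for slices up to 5 mm and twice the slice above that (15 mm at 7.5 mm). Follow smaller lesions as non-target. Stating a maximum slice thickness would also help.

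Add a row to the overall response table for subjects with non-target disease only. Footnote 15 and the non-target rules already allow for subjects without measurable disease, but the table has no row for them; the nearest one (target not evaluable, non-target not progressed) returns not evaluable.

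Sample size, cut-offs, alpha and power do not change. The cost is that a few subjects whose only uninjected lesion is under 10 mm would be assessed by the qualitative non-target rules and could not be scored PR. Without measurable disease those rules compare progression with a 20% increase in diameter, which is 1 mm on a 5 mm lesion. The existing requirement that non-target progression be unequivocal then has to guard against false PD.

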1. LIST OF ABBREVIATIONS

| Abbreviation | Meaning |
|--------------|---|
| AE | Adverse event |
| ATC | Anatomical Therapeutic Chemical |
| Bpm | Beats per minute |
| °C | Degrees Celsius |
| CR | Complete response |
| CRF | Case Report Form |
| CT | Computed tomography |
| CV | Coefficient of variation |
| CTC, CTCAE | Common Terminology Criteria for Adverse Events |
| DCR | Disease control rate |
| ECG | Electrocardiogram |
| ECOG | Eastern Cooperative Oncology Group |
| °F | Degrees Fahrenheit |
| HER2 | Human epidermal growth factor receptor 2 |
| irCR | Complete disappearance of all lesions (whether measurable or not, and no new lesions) confirmation by a repeat, consecutive assessment no less than 4 weeks from the date first documented |
| irDCR | Immune-related Disease Control Rate |
| irORR | Immune-related Overall Response Rate |
| irPD | Increase in tumor burden $\geq 25\%$ relative to nadir (minimum recorded tumor burden) confirmation by a repeat, consecutive assessment no less than 4 weeks from the date first documented |
| irPR | Decrease in tumor burden $\geq 50\%$ relative to baseline confirmed by a consecutive assessment at least 4 weeks after first documentation |
| irRC | Immune-Related Response Criteria |
| irSD | Not meeting criteria for irCR or irPR, in absence of irPD |
| MedDRA | Medical Dictionary for Regulatory Activities |
| mmHg | Millimeter(s) of mercury |
| N | Number of observations |
| n | Number of subjects |
| NCI | National Cancer Institute |
| ORR | Objective response rate |

| Abbreviation | Meaning |
|--------------|--|
| OS | Overall Survival |
| PD | Progressive Disease |
| PFS | Progression-Free Survival |
| PR | Partial response |
| RECIST | Response Evaluation Criteria in Solid Tumors |
| SAE | Serious adverse event |
| SAP | Statistical Analysis Plan |
| SAS | Statistical Analysis System |
| SD | Stable Disease |
| Std dev | Standard Deviation |
| SPD | Sum of perpendicular diameters |
| SRC | Safety review committee |
| TEAE | Treatment-emergent adverse event |
| Vp | Viral particles |
| WHO | World Health Organization |

2. PURPOSE

The purpose of this statistical analysis plan (SAP) is to ensure that the data listings, summary tables, and figures that will be produced, and the statistical methodologies that will be used, are complete and appropriate to allow valid conclusions regarding the study objectives.

3. PRIMARY OBJECTIVES

- To evaluate the safety and tolerability of one cycle of Ad-RTS-hIL-12 immunotherapy a) following a first-, second-, or third-line standard treatment in HER2-negative (HER2-) subjects, or b) together with a first-, second-, or third-line anti-HER2 antibody therapy in HER2-positive (HER2+) subjects as defined by Section 12.4.2 in the protocol.

4. SECONDARY OBJECTIVES

- To estimate the progression rate at 12 weeks after the start of one cycle of Ad-RTS-hIL-12 immunotherapy
- To evaluate the overall response rate (ORR), defined as the rate of complete response (CR) plus the rate of partial response (PR) at 12 weeks following the start of Ad-RTS-hIL-12 immunotherapy
- To evaluate the disease control rate (DCR), defined as the proportion of subjects who have a CR, PR, or stable disease at 12 weeks following the start of one cycle of Ad-RTS-hIL-12 immunotherapy
- To evaluate the number of subjects whose baseline tumor status (stable disease or PR) improves to PR or better at 12 weeks following the start of Ad-RTS-hIL-12 immunotherapy
- To compare radiographic responses by irRC with conventional reporting by RECIST
- To explore the impact of treatment on tumor and blood immune biomarkers

5. STUDY DESIGN

5.1. Endpoints:

5.1.1. Primary Endpoint

The primary endpoint is the safety assessment of Ad-RTS-hIL-12 immunotherapy

a) following a first-, second-, or third-line standard treatment in HER2- subjects, or b) together with a first-, second-, or third-line anti-HER2 antibody therapy in HER2+ subjects as defined by Section 12.4.2.

5.1.2. Secondary Endpoints

Secondary endpoints are as follows:

- The proportion failed by 12 weeks is denoted as the progression rate survival and is derived based on the sum of progression events, death events, and subjects who discontinue the trial due to an Adverse event (AE).
- The ORR, defined as the rate of CR plus the rate of PR at 12 weeks following the start of Ad-RTS-hIL-12 immunotherapy
- The DCR, defined as the proportion of subjects who have a CR, PR, or stable disease at 12 weeks following the start of one cycle of Ad-RTS-hIL-12 immunotherapy
- The number of subjects whose baseline tumor status (stable disease or PR) improves to PR or better at 12 weeks following the start of Ad-RTS-hIL-12 immunotherapy
- The radiographic responses by irRC with conventional reporting by RECIST
- Tumor and serum immune biomarkers

5.2. Overall Study Design

This is a single-arm, single-center Phase Ib/II study to examine the safety, tolerability, and preliminary efficacy of providing one cycle of Ad-RTS-hIL-12 immunotherapy following achievement of stable disease or PR on standard first-, second-, or third-line chemotherapy in breast cancer subjects. The subject population includes subjects with locally advanced or metastatic breast cancer of all subtypes. The safety of this therapy and the preliminary evidence of efficacy will guide further studies. Subjects are required to be in stable disease or PR after completion of a minimum of 12 weeks on standard chemotherapy. Subjects who have progressive disease (PD) or a CR after standard chemotherapy are not eligible for the study. Following entry into the trial, subjects will go on a treatment holiday from the standard chemotherapy and enter an immunotherapy phase of treatment.

Scans will be conducted 6 and 12 weeks after the start of Ad-RTS-hIL-12 immunotherapy for determination of tumor response. Radiographic PD at Week 6 must be confirmed at least 4 weeks later, either at Week 12 or earlier if clinically necessitated. In cases of slow tumor growth, the investigator may wait until confirmation of PD at 12 weeks to resume chemotherapy. In cases of unequivocal progression, the investigator may resume chemotherapy prior to 12 weeks and the subject will be considered as treatment failure at 12 weeks.

Upon completion of Week 12, subjects who are considered to have stable disease or better will enter long-term follow-up for up to an additional 36 weeks. In the long-term follow-up period, scans will be performed at 18, 24, 36, and 48 weeks until a radiographic response of PD is confirmed.

The assessment of response will be based on Response Evaluation Criteria in Solid Tumors (RECIST) v1.1 using tumor measurements from contrast-enhanced computed tomography (CT). Tumor response will also be assessed by Immune-Related Response Criteria (irRC) ([Wolchok et al, 2009](#)). Eligible subjects will also be asked to consent to allow ZIOPHARM to obtain scans and tumor measurements taken both a) prior to initiating the prestudy standard chemotherapy and b) after a minimum of 12 weeks of prestudy standard chemotherapy, and not more than 4 weeks prior to study enrollment, in order to confirm their stable disease or PR study entry status.

For subjects with HER2- disease, the Ad-RTS-hIL-12 immunotherapy is intended to be given as a chemotherapy holiday, for example, to avoid intolerable or undesirable toxicity of the standard therapy. Ad-RTS-hIL-12 immunotherapy must be started within 4 weeks of stopping the prestudy standard chemotherapy.

Subjects with HER2+ disease will receive Ad-RTS-hIL-12 immunotherapy in conjunction with first-, second-, or third-line anti-HER2 antibody therapy, i.e., subjects may continue anti-HER2-directed antibody therapy during the study period. Anti-HER2 antibody therapy will be administered according to the manufacturer's recommendations. Subjects with HER2+ breast cancer who continue the anti-HER2 antibody therapy need to recover from any anti-HER2-related AE/serious adverse event (SAE), i.e., the event must have resolved to Grade 1 or baseline, before starting Ad-RTS-hIL-12 immunotherapy.

The Ad-RTS-hIL-12 immunotherapy cycle is a 21-day cycle comprised of investigational product administration on Days 1 through 7 followed by rest on Days 8 through 21. On Day 1, enrolled subjects will receive the first dose of veledimex followed 3 hours \pm 3 hours later by an intratumoral injection of Ad-RTS-hIL-12. The veledimex will continue to be given once daily on Days 2 through 7. The safety evaluation will be based on the occurrence of related, treatment refractory Grade 3 and 4 AEs within 21 days following the start of Ad-RTS-hIL-12 immunotherapy. A post-treatment safety assessment visit will be conducted on Day 21.

Immunologic biomarkers of response in blood and tumor will also be explored. Full details of the study design can be found in the protocol.

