4.1.1 Study Design and Treatment Arm Expansion Procedure

4.1.1.1 Overall Study Design

This is a randomized, open-label, Phase II study of Ad-RTS-hIL-12 monotherapy or Ad-RTS-hIL-12 in combination with palifosfamide in subjects with recurrent/metastatic breast cancer with accessible lesions.

Two treatment arms will be assessed for safety, followed by random assignment to Ad-RTS-hIL-12 monotherapy or combination therapy. Each subject will be treated for up to 6 treatment cycles, with each cycle being 21 days in duration.

Safety and tolerability will be assessed by the incidence and severity of AEs as determined by National Cancer Institute (NCI) Common Terminology Criteria for Adverse Events (CTCAE) v4.03. A SRC comprised of the Medical Monitor, enrolling Principal Investigators (PIs), and Sponsor representatives, will be convened to review safety information and to decide upon further subject enrollment.

The antitumor activity of study treatment will be assessed according to mRECIST v1.1 guidelines.³¹ ([Appendix 4](#))

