8.4 Study Endpoints

8.4.1 Primary Efficacy Endpoint

The primary efficacy endpoint is the 16-week PFS rate, calculated as the number of subjects who had not progressed or died prior to 16 weeks from the date of their first dose, divided by the number of subjects in the study arm. Subjects who neither progressed nor died, but had their last tumor assessment prior to 16 weeks, will not be categorized as progression-free and will not be included in the numerator. Progressive disease (PD) will be determined by mRECIST v1.1 (please refer to [Appendix 4](#)).

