8.6.4 Efficacy Analyses

The Efficacy Evaluable Population will be used for the analyses of efficacy data by study arm.

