	
Defined as clinically significant. 
Clinical significance should relate to the size and location of the new lesion, such as new brain involvement, significant vascular invasion or compression.
 
Any lesion that does not meet the above criteria should be considered an equivocal new lesion that does not justify in isolation an overall assessment of progression at that time point. Such equivocal new lesions should be re-evaluated at the next time point.
	

PROTOCOL AMENDMENT SUMMARY

Protocol Title: A Phase II Randomized, Open-Label Study of Ad-RTS-hIL-12 Monotherapy or Combination with Palifosfamide in Subjects with Recurrent/Metastatic Breast Cancer and Accessible Lesions

Protocol Number: ATI001-201

Study Drugs: INXXN-2001 (Ad-RTS-hIL-12)
INXXN-1001 (oral activator ligand)
Palifosfamide

Date of Protocol: Amendment 2: 17 June 2013
Amendment 1: 04 Jan 2013
Original protocol: 17 Aug 2012

NOTE TO INVESTIGATORS

Amendment 2 dated 17 June 2013 will be used to conduct the study in place of any preceding version of this protocol.

CONFIDENTIAL

Tabular Summary of Revisions Implemented in the Amended Protocol

Section in Amended Protocol	Revised or Deleted Text/Section	Rationale for Change
Title Page, Page Headings and Footers	Amendment 2: 17 June 2013	Updated Protocol Amendment
Abbreviations and Definitions of Terms	Several new abbreviations were included: eg, MCV , RXR .	Clarify abbreviations

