8.3. Previous and Concomitant Medication

Concomitant medications recorded during the study will be coded using the WHO-Drug version March 2016. Details of concomitant medications will be listed.

Medications will be tabulated according to whether they were being taken prestudy and/or during the study. Medications received in the period preceding consent (~28 days) in addition to those ongoing at Screening will be captured in the Case Report Form (CRF). Concomitant medications are any that were being taken on or after the first dose of study medication until completion of veledimex dosing. If the start and stop dates of the concomitant medications do not clearly define the period(s) during which a medication was taken, it will be assumed to have been a concomitant medication.

Previous and concomitant medications will be tabulated by preferred term and ATC term 2.

Non-pharmacological concomitant measures (e.g., procedures) will be listed.

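### The supplied SAP describes a different study from the supplied protocol, so the governing pair must be named; separately, the protocol's primary-rate denominator and its Arm A power statement need reconciling

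*SAP*

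**What the plan says.** The SAP (Section 5.2) states: "This is a single-arm, single-center Phase Ib/II study to examine the safety, tolerability, and preliminary efficacy of providing one cycle of Ad-RTS-hIL-12 immunotherapy". Subjects enter with stable disease or partial response after chemotherapy; those with progression are ineligible. Safety is the only primary endpoint (Section 5.1.1). Efficacy is read at week 12 by RECIST v1.1 and irRC (Section 10) and summarised by HER2 status and overall (Section 6). At most 40 subjects are treated, and no hypothesis is set (Section 5.4).

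The protocol (Section 4.1.1.1) states: "This is a randomized, open-label, Phase II study of Ad-RTS-hIL-12 monotherapy or Ad-RTS-hIL-12 in combination with palifosfamide". It plans about 30 centres, up to 6 cycles and up to 62 subjects, who must have failed or progressed on prior chemotherapy (synopsis; Section 5.1). Safety and the 16-week PFS rate by mRECIST v1.1 are both primary. Each arm is analysed separately under a Simon two-stage rule (synopsis; Section 8.1).

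On the denominator, Section 8.4.1 counts subjects free of progression and death "16 weeks from the date of their first dose, divided by the number of subjects in the study arm", whereas Section 8.6.4 says "The Efficacy Evaluable Population will be used for the analyses of efficacy data by study arm". Section 8.3 limits that population to treated subjects with at least one response evaluation after screening.

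On Arm A, the synopsis requires at least 1 of the first 6 subjects to be progression-free at week 16 before Stage 1 is filled to 13. Section 8.1 gives 80% power for 13 then 33 subjects and does not mention that look.

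**The concern.** Protocol Section 8.8 calls for a formal analysis plan before database lock that indicates departures from the protocol's analyses. The supplied SAP lists no departures, yet it differs in every defining element. Applied to this trial, it would give week-12 rates by HER2 status and no primary efficacy result for Arm A or Arm C. If a later protocol governs instead, the stage rules reviewed here may be superseded, and writing a new SAP for Arms A and C would be wasted effort. The pairing therefore comes first.

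The other two points belong to the protocol and would stand with any SAP. One leaves the primary rate with two possible denominators. The other leaves the stated Arm A power describing a design without the first look.

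**Working it through.** **1. The two plans side by side**

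| Element | Protocol | SAP |
|---|---|---|
| Design | Randomised, Arms A and C, about 30 centres | One arm, one centre |
| Treatment | Up to 6 cycles; palifosfamide in Arm C | One cycle; palifosfamide not mentioned |
| Entry | Failed or progressed on chemotherapy | SD or PR; PD ineligible |
| Primary endpoint | Safety and 16-week PFS rate | Safety only |
| Response criteria | mRECIST v1.1 | RECIST v1.1 and irRC |
| Groups | By arm | By HER2 status and overall |
| Size and basis | Up to 62; Simon rules | At most 40; interval width |
| Protocol references cited | Appendices are 13.1 to 13.6 | Sections 12.4.2 and 9.2.2.7, Appendix 16.3: none exists here |

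Scan timing also differs. Footnote 15 to protocol Tables 2A and 2B says "Tumor response assessments will occur at 12 weeks and 16 weeks (C5D1 and C6D7", plus week 24. Cycle 6 Day 7 is 5 × 21 + 7 = day 112, which is week 16. The SAP scans at weeks 6 and 12, and in follow-up "scans will be performed at 18, 24, 36, and 48 weeks". No SAP scan falls at week 16.

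**2. Each document's own figures reproduce**

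Protocol: go-ahead probability = Σ over x ≥ r1 of Bin(x; n1, p) × P[Bin(n − n1, p) ≥ r − x].

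- Arm A, at least 3/13 then at least 9/33: 0.041 at p = 0.15 and 0.808 at p = 0.35.
- Arm C, at least 6/12 then at least 15/26: 0.047 at p = 0.40 and 0.809 at p = 0.65.

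Both agree with the 80% power and one-sided 5% level in Section 8.1.

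SAP: the widest exact 95% interval at n = 40 is at 20/40, 0.338 to 0.662. Its half-width is (0.662 − 0.338)/2 = 0.162, against 0.16 stated.

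Each plan is consistent with itself. The mismatch is not an arithmetic slip in either.

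**3. Arm A with the first look binding**

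Let x be the successes among the first 6 and y those among the next 7. Go-ahead probability = Σ over x ≥ 1 and x + y ≥ 3 of Bin(x; 6, p) × Bin(y; 7, p) × P[Bin(20, p) ≥ 9 − x − y].

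- p = 0.35: 0.780, against 0.808 without the look.
- p = 0.15: 0.039, against 0.041 without the look.

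The chance of stopping at that look is 0.65^6 = 0.075 at the target rate and 0.85^6 = 0.377 at the rate of no interest. The power in Section 8.1 is reproduced only without the look.

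**4. Denominator**

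The documents give no non-evaluable rate. Assume 0 to 4 subjects per arm have no response evaluation after screening, and hold the success count at the go threshold.

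- Arm A: 9/33 = 27.3% rises to at most 9/29 = 31.0%.
- Arm C: 15/26 = 57.7% rises to at most 15/22 = 68.2%.

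The direction is fixed. Subjects without an evaluation cannot be in the numerator under Section 8.4.1, so removing them can only raise the rate.

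**The case against.** The strongest reply is that this may be only a filing error. The title pages are not in the text available, and the body does not say which protocol the SAP serves. The protocol itself fixes the endpoint, the estimators (Section 8.6.4.1) and the stage rules, so the trial has a rule. All of that stands. It limits the point to a mismatch of documents, not a criticism of analyses chosen for Arms A and C. It does not make this SAP usable with this protocol.

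A reader might infer from the dates that the SAP belongs to a later protocol. The SAP says "Concomitant medications recorded during the study will be coded using the WHO-Drug version March 2016", and the last supplied amendment notice says "Amendment 2 dated 17 June 2013 will be used to conduct the study in place of any preceding version of this protocol". The documents do not support that inference. A dictionary version is not a SAP date, Section 8.8 asks only for a plan before database lock, and the study was expected to run about 34 months. The dates are compatible with a SAP written late for this protocol.

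A reader might also infer that the denominator could change the Arm C decision. With 2 non-evaluable subjects, the exact lower bound at the threshold would move from 0.369 (15/26) to 0.406 (15/24), past the 40% rate of no interest. The documents do not support that either. The go rule is a count, and 15/26 already passes with a lower bound below 40%. That bound is a one-sided 2.5% limit, while Section 8.1 tests at one-sided 5%. The number 2 is assumed, and Sections 4.1.5 and 5.4 allow subjects to be added when others stop early for reasons other than progression, so denominators need not shrink.

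On the first look, Section 8.1 is silent and does not contradict the synopsis. Part of the synopsis's Arm A design text is missing from the copy available and may say whether the look binds. The loss is under 3 percentage points of power, and type I error falls.

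**Conclusion.** Wrong as written. The supplied SAP does not match the supplied protocol and cannot yield its primary efficacy analysis: the analysis by arm, the 16-week mRECIST rate and the stage rules are all absent. This rests on the body text and the unmatched section references. It does not rest on dates, and it does not settle which study the SAP belongs to.

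Two smaller protocol points hold separately. The primary rate has two denominators; the size of the effect depends on a non-evaluable rate that the documents do not give, and no count-based decision turns on the interval bound. Arm A power is about 78% (type I error 0.039) if the look at 6 is binding, against the stated 80%. These probabilities describe the count rule only, because the synopsis also lets secondary endpoints enter futility decisions.

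**What to change.** 1. **Pairing.** State which protocol and SAP govern. If a later protocol governs, supply it. If the SAP belongs to another study or was misfiled, withdraw it. If this protocol governs, replace the SAP with one that analyses Arms A and C by the 16-week mRECIST v1.1 PFS rate. It should carry the exact 95% interval and the Kaplan-Meier estimate with Greenwood interval from Section 8.6.4.1, and the stage rules (3/13 then 9/33; 6/12 then 15/26). It should list any deviations as Section 8.8 requires.
2. **Denominator (protocol).** Reconcile Sections 8.4.1 and 8.6.4. Use all subjects in the arm, as Section 8.4.1 defines, for the primary rate and its exact interval, and report the Efficacy Evaluable Population as a sensitivity analysis.
3. **Arm A power (protocol).** Reconcile the synopsis with Section 8.1. Either restate Arm A power as about 78% with type I error 0.039, or state that the look at the first 6 is non-binding.

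The cost is document work only, with no added subjects or visits.
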